2. INTRODUCTION

This statistical analysis plan (SAP) provides the detailed methodology for summary and statistical analyses of the data collected in Study C3391007. This document may modify the plans outlined in the protocol; however, any major modifications of the primary endpoint definition or its analysis will also be reflected in a protocol amendment.

This SAP covers the analyses to be performed for the primary analysis that is to occur when all participants have completed visits through 4 months (or withdrawn from the study prior to 4 months). The C3391007 Data Access Plan describes the reporting strategy that appropriately maintains the blinded treatment assignment in Studies C3391003 and C3391002.

Statistical analyses will be performed using cleaned case report form (CRF) data as well as non-CRF data (i.e., blood samples data and banked biospecimens).

2.1. Study Objectives and Endpoints

Primary Objective:	Primary Endpoint:
To quantify the proportion of participants (previously seronegative for neutralizing antibody [NAb] to adeno associated virus serotype 9 [AAV9]) who develop NAb to AAV9 (i.e., seroconversion)	Development of NAb to AAV9 (i.e., NAb seroconversion) as defined by an increase of ≥ 6 -fold above Baseline titer in participants with a detectable, but negative test (i.e., titer ≥ 1 and < 4) for NAb to AAV9 at Baseline. If there is an undetectable titer at Baseline (i.e., titer < 1), then development of NAb to AAV9 as defined by a NAb to AAV9 titer.
Secondary Objective:	Secondary Endpoint:
To quantify the proportion of participants (previously seronegative for anti-drug antibody [ADA] to AAV9) who develop ADA to AAV9.	Development of ADA to AAV9 (i.e., ADA seroconversion) defined by a titer ≥ 300 in participants with a negative test (i.e., titer < 50) for ADA to AAV9 at Baseline.
Exploratory Objectives:	Exploratory Endpoints:
To quantify the proportion of participants (previously seropositive for NAb to AAV9) who have an increase in the NAb to AAV9 titer.	NAb to AAV9 titer ≥ 6 -fold higher than Baseline titer in participants who are seropositive (i.e., titer ≥ 4) for NAb to AAV9 at Baseline.
To quantify the proportion of participants (previously seropositive for ADA to AAV9) who have an increase in the ADA to AAV9 titer.	ADA to AAV9 titer ≥ 6 -fold higher than Baseline titer in participants who are seropositive (i.e., titer ≥ 50) for ADA to AAV9 at Baseline.

To quantify the proportion of participants who seroconvert and have detectable fordadistrogene movaparvovec vector deoxyribonucleic acid (DNA) in blood.	Detectable fordadistrogene movaparvovec vector DNA in participants who seroconvert via either ADAs or NAbs.
--	---

Note that the NAb analytical report delivers a titer value (based on interpolation of NAb activity at several dilutions), as well as a clinical assessment of “positive” or “negative” based on the NAb activity at a specific 1:4 dilution. Because of the potential for discrepancy between the quantitative result and the clinical result, the clinical result will be disregarded in this study and all analyses will be derived based on the titer value from the report.

2.2. Study Design

C3391007 is single center, low-interventional study to include approximately 50 to 250 participants and is designed to estimate the likelihood of NAb seroconversion to AAV9 because of exposure to shed viral vector material released by a Duchenne muscular dystrophy (DMD) participant treated with fordadistrogene movaparvovec in clinical studies. This study will include participants who live or work in the same household as a participant in one of the fordadistrogene movaparvovec interventional studies, which may include study C3391003, C3391002, C3391008, or C3391001. Up to 5 participants from the same household may be enrolled.

3. ENDPOINTS AND BASELINE VARIABLES: DEFINITIONS AND CONVENTIONS

Note that the NAb analytical report delivers a titer value (based on interpolation of NAb activity at several dilutions), as well as a clinical assessment of “positive” or “negative” based on the NAb activity at a specific 1:4 dilution. Because of the potential for discrepancy between the quantitative result and the clinical result, the clinical result will be disregarded in this study and all analyses will be derived based on the titer value from the report.

3.1. Primary Endpoint

- Development of NAb to AAV9 (i.e., NAb seroconversion) defined as either of the following:
 - an increase of \geq 6-fold above Baseline titer in participants with a detectable, but negative test (i.e., titer ≥ 1 and < 4) for NAb to AAV9 at Baseline or
 - a NAb to AAV9 titer ≥ 6 in participants with an undetectable titer at Baseline (i.e., titer < 1).

The response of developing NAb seroconversion will be derived as Positive or Negative.

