9.2. Sample Size Determination

Approximately 50 to 250 participants will be enrolled. [Table 1](#) below shows the expected precision, defined as the upper and lower 95% confidence limits, of the estimate of the proportion of participants who are negative for NAb to AAV9 at Baseline and who develop NAb to AAV9 post-Baseline for various numbers of enrolled participants. These calculations assume that 75% of the participants will be seronegative for NAb to AAV9 at Baseline.

Table 1. 95% CI of the Estimate of the Proportion of Participants who are NAb Seronegative to AAV9 at Baseline and who Seroconvert to AAV9 Post-Baseline

Total Enrolled in C3391007	Interventional study patient who received fordadistrogene movaparvovec				Interventional study patient who received placebo			
	N ^a	Number NAb seronegative to AAV9 at Baseline ^b	Percent who seroconvert to AAV9	95%, CI ^c	N ^a	Number NAb seronegative to AAV9 at Baseline ^b	Percent who seroconvert to AAV9	95%, CI ^c
50	33	25	1%	(0, 4.9)	17	13	1%	(0, 6.4)
			5%	(0, 13.5)				
			10%	(0, 21.8)				
			25%	(8.0, 42.0)				
			50%	(30.4, 69.6)				
100	66	50	1%	(0, 3.8)	34	26	1%	(0, 4.8)
			5%	(0, 11.0)				
			10%	(1.7, 18.3)				
			25%	(13.0, 37.0)				
			50%	(36.1, 63.9)				
150	100	75	1%	(0, 3.3)	50	38	1%	(0, 4.2)
			5%	(0.1, 9.9)				
			10%	(3.2, 16.8)				
			25%	(15.2, 34.8)				
			50%	(38.7, 61.3)				
200	133	100	1%	(0, 3.0)	67	50	1%	(0, 3.8)
			5%	(0.7, 9.3)				
			10%	(4.1, 15.9)				
			25%	(16.5, 33.5)				
			50%	(40.2, 59.8)				
250	167	125	1%	(0, 2.7)	83	62	1%	(0, 3.5)
			5%	(1.2, 8.8)				
			10%	(4.7, 15.3)				
			25%	(17.4, 32.6)				
			50%	(41.2, 58.8)				

a. Assumes, on average two thirds of patients are treated with fordadistrogene movaparvovec and one third are treated with placebo across the interventional studies.

b. Assumes 75%, are NAb seronegative at Baseline.

c. Assumes all participants within households and between households are independent.

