1. VERSION HISTORY

This Statistical Analysis Plan (SAP) V3 for study C3391007 is based on the protocol amendment #1 dated 05 Apr 2022.

Table 1. Summary of Changes

Version/ Date	Associated Protocol Amendment	Rationale	Specific Changes
V3/ 17 May 2024	Protocol amendment #1	To clarify that height was not collected according to protocol and age category summary is not needed due to small sample size	Section 3.4 Removed age category groups in demographic characteristics Removed height and BMI measurement in baseline summary
		To update statistical analysis method due to small number of enrolled patients	Section 5.2.2 Removed model based analysis for confidence interval for proportion Sections 6.1, 6.2, 6.3 Removed GEE analysis and 95%CI from the analysis and summary Section 6.4 Removed subgroup analysis
		To clarify the summary results needed for interim analysis	Section 7 Added “In order to minimize possibility of unblinding internal study team, the external vendor will provide only the percent of participants whose family members received fordadistrogene movaparvovec and converted.”

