3.2. Secondary Endpoint

- Development of ADA to AAV9 (i.e., ADA seroconversion) defined by a titer ≥ 300 in participants with a negative test (i.e., titer < 50) for ADA to AAV9 at Baseline.

The response of developing ADA seroconversion will be derived as Positive or Negative.

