3.3. Exploratory Endpoints

- Boosted NAb to AAV9 defined by NAb to AAV9 titer \geq 6-fold higher than Baseline titer in participants who are seropositive (i.e., titer ≥ 4) for NAb to AAV9 at Baseline.
 - Note that the upper limit of quantification of AAV9 NAb titer is 32,000, and if the baseline titer is $>5,333$, a 6-fold increase of titer cannot be determined. Therefore, NAb seropositive subjects with baseline NAb titer $>5,333$ will be removed from this particular exploratory analysis.
- Boosted ADA to AAV9 defined by ADA to AAV9 titer \geq 6-fold higher than Baseline titer in participants who are seropositive (i.e., titer ≥ 50) for ADA to AAV9 at Baseline.
- Detectable fordadistrogene movaparvovec vector DNA in blood defined as a detectable fordadistrogene movaparvovec vector DNA in participants who seroconvert via either ADAs or NAb.

The responses of the exploratory endpoints above will be derived as Positive or Negative.

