6. ANALYSES AND SUMMARIES

6.1. Primary Endpoint

6.1.1. Development of NAb to AAV9

- Analysis Set: Immunogenicity ([Section 4](#))
- Analysis methodology: Descriptive statistics ([Section 5.2.1](#)) by visit and overall
- Missing data: Missing data will not be imputed ([Section 5.3](#))

DMB02-GSOP-RF02 5.0 Statistical Analysis Plan Template 05-Dec-2019

PFIZER CONFIDENTIAL

Page 9

TMF Doc ID: 98.03

- Proportions will be provided separately for visits 3 and 4, and overall at any time during the study by the study treatment (fordadistrogene movaparvovec fordadistrogene movaparvovec or placebo) of the interventional study participant. For overall, the response of the participant will be considered as positive if any values in visits 3 and 4 are positive; otherwise the response will be considered as negative.

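### Is the primary NAb result unsound because no planned output counts seronegative contacts who reach titer 4 without meeting the 6-fold or titer-6 rule?

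*SAP*

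**What the plan says.** The Protocol (Section 3) and SAP 3.1 give the primary endpoint in two parts. With an undetectable Baseline (titer below 1), a contact converts at titer 6 or more. With Baseline from 1 to below 4, conversion needs a rise of at least "6-fold above Baseline titer in participants with a detectable, but negative test". The response is then recorded as Positive or Negative. (SAP 2.1 leaves out the number for the undetectable part. SAP 3.1 and the Protocol both supply 6.)

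The neighbouring endpoints use the same factor:

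- SAP 3.2: "Development of ADA to AAV9 (i.e., ADA seroconversion) defined by a titer" of at least 300, starting from below 50.
- SAP 3.3, boosted NAb: at least 6-fold, "in participants who are seropositive (i.e., titer ≥ 4) for NAb to AAV9 at Baseline".
- SAP 3.3, vector DNA: "detectable fordadistrogene movaparvovec vector DNA in participants who seroconvert via either ADAs or NAb".

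On reporting, SAP 6.1.1 says: "Proportions will be provided separately for visits 3 and 4, and overall at any time during the study by the study treatment" of the interventional patient. Anything not Positive is Negative. SAP Section 3 also sets aside the laboratory's own call at the 1:4 dilution: "the clinical result will be disregarded in this study and all analyses will be derived based on the titer value from the report". SAP 6.4 plans no subgroup analyses.

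**The concern.** The Baseline line is at titer 4, but the conversion line is higher, at 6 to just under 24 depending on where the contact started. Someone who goes from 2 to 11, from 3.5 to 20, or from below 1 to 5 finishes above the level the study itself labels seropositive, yet is counted Negative. They cannot enter boosted NAb, which needs Baseline 4 or more. They reach the vector-DNA endpoint only if they convert on ADA. The laboratory call that might have flagged them is disregarded, and SAP 6.1 names no titer summary or titer listing.

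The study is meant to tell families how likely a household contact is to develop NAbs. If several contacts sat in this band, a reported rate of 0% would look more reassuring than the titers behind it.

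**Working it through.** **The plan's own figures.** Protocol Table 1 is the only planning calculation for this endpoint. It is a Wald interval, p ± 1.96·√(p(1−p)/n), cut at 0.

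- n = 25, p = 10%: 10 ± 1.96 × 6.0 = 10 ± 11.76, giving 0 to 21.8 as printed.
- n = 125, p = 5%: 5 ± 1.96 × 1.949 = 5 ± 3.82, giving 1.2 to 8.8 as printed.

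All 29 distinct combinations of n and percentage match to rounding. The factor of 6 is also used consistently: 300/50 = 6 for ADA, and 32,000/6 = 5,333, which is the exclusion limit stated for boosted NAb.

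**The band.** The required titer is T(b) = 6 for Baseline b below 1, and 6b for b from 1 to below 4. The uncounted band is 4 up to T(b).

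| Baseline | Required titer | Band | Rise that just reaches 4 |
|---|---|---|---|
| <1 | 6 | 4 to <6 | – |
| 1 | 6 | 4 to <6 | 4.0-fold |
| 2 | 12 | 4 to <12 | 2.0-fold |
| 3 | 18 | 4 to <18 | 1.33-fold |
| 3.9 | 23.4 | 4 to <23.4 | 1.03-fold |

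The band exists for every seronegative Baseline. It is wide only where Baseline is already close to 4, and there reaching 4 takes hardly any rise.

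**Possible size.** Table 1 rests on this: "These calculations assume that 75% of the participants will be seronegative for NAb to AAV9 at Baseline". At 50 enrolled that gives 25 and 13 seronegative contacts, so one contact in the band is 1/25 = 4.0 points or 1/13 = 7.7 points. At 250 enrolled it is 1/125 = 0.8 or 1/62 = 1.6 points. The documents give no titer distribution, so the count itself is unknown and may be zero.

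**Would a count at titer 4 or more be better?** The documents give no assay precision. Assume log-normal error with geometric SD g = 1.2, 1.5 or 2.0, a true titer t that does not change, and two post-Baseline samples. The chance that at least one reads 4 or more is 1 − Φ(ln(4/t)/ln g)².

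| True titer | g = 1.2 | g = 1.5 | g = 2.0 |
|---|---|---|---|
| 0.5 | 0.0% | 0.0% | 0.3% |
| 1 | 0.0% | 0.1% | 4.5% |
| 2 | 0.0% | 8.5% | 29.2% |
| 3 | 11.1% | 42.1% | 56.3% |

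For the planned rule at true titer 3, the matching chance is the average of 1 − Φ(ln(T(B)/3)/ln g)² over measured Baselines B below 4. By simulation this is 0.0%, 0.2% and about 7.5%.

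Splitting by measured Baseline does not fully remove the noise. With g = 2.0, a contact with true titer 2 reads below 1 with probability Φ(ln(1/2)/ln 2) = Φ(−1) = 15.9%, and then still has a 29.2% chance of a later reading of 4 or more.

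**Is there a conflict between sections?** The objective is the proportion of previously seronegative contacts who develop NAb. Protocol Section 3 and SAP 3.1 define that event in the same way, and SAP 6.1.1 estimates that proportion. Titer 4 is used only to classify contacts at Baseline. Protocol 2.2.2 links likely exclusion from AAV9 therapy to NAb seroconversion and gives no titer; no other section ties a post-Baseline titer of 4 to any consequence.

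**The case for a change.** The best argument for the concern is that the two-part rule can rank final levels oddly: below 1 to 6 is Positive, while 3.5 to 20 (5.7-fold) is Negative. Summary rates may be passed to participants and investigators (Protocol 9.6, SAP 7). The current SAP also dropped the model and the intervals, with the reason "To update statistical analysis method due to small number of enrolled patients", so a bare percentage carries the message. An extra row and a short listing would cost little, since the titers are already measured.

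The facts in this argument stand. SAP 6.1.1 does cite the general descriptive methods of SAP 5.2.1, which cover continuous variables, but the only variable it names is the Positive/Negative response. I do not read that as a planned titer summary.

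The inference does not follow. The odd ranking comes from defining development of antibody as a rise from the contact's own starting point. That suits a study of response to exposure, where 3.9 to 4.1 should not count as an event. Any yes/no endpoint leaves changes below its threshold uncounted. Splitting an added row by the two Baseline ranges would give 2 ranges × 2 treatment groups × 3 time summaries = 12 cells, in a study whose SAP removed subgroup analyses because enrolment was small. The titers are not lost either: Protocol 6.2 withholds individual results only until the contributing blinded studies are unblinded, and Protocol 10.1.5 provides for access to patient-level data.

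**Conclusion.** The concern does not hold. The band is real and no named output shows it, but the plan states one definition, uses the same factor of 6 across its antibody endpoints, and estimates what its objective asks for. Followed as written, it gives a sound answer to that objective.

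Two things would have to be true for this to be a flaw. A post-Baseline titer of 4 would need a meaning that the documents do not give it, and a count at that level would need to be clearly more informative than the planned rule. The second is doubtful: under the assumed noise, 11% to 56% of unchanged contacts at true titer 3 would be counted, against 0% to about 7.5% under the planned rule. Where Baseline is below 1 and noise matters least, the band is only 4 to below 6.

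The noise figures depend on assumed precision. The 4.0 and 7.7 points per contact depend on Table 1's planning counts at 50 enrolled. A titer listing at final reporting would be a reasonable extra, but its absence from the SAP is a matter of preference.

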3.2. Secondary Endpoint

- Development of ADA to AAV9 (i.e., ADA seroconversion) defined by a titer ≥ 300 in participants with a negative test (i.e., titer < 50) for ADA to AAV9 at Baseline.

The response of developing ADA seroconversion will be derived as Positive or Negative.

3.3. Exploratory Endpoints

- Boosted NAb to AAV9 defined by NAb to AAV9 titer \geq 6-fold higher than Baseline titer in participants who are seropositive (i.e., titer ≥ 4) for NAb to AAV9 at Baseline.
 - Note that the upper limit of quantification of AAV9 NAb titer is 32,000, and if the baseline titer is $>5,333$, a 6-fold increase of titer cannot be determined. Therefore, NAb seropositive subjects with baseline NAb titer $>5,333$ will be removed from this particular exploratory analysis.
- Boosted ADA to AAV9 defined by ADA to AAV9 titer \geq 6-fold higher than Baseline titer in participants who are seropositive (i.e., titer ≥ 50) for ADA to AAV9 at Baseline.
- Detectable fordadistrogene movaparvovec vector DNA in blood defined as a detectable fordadistrogene movaparvovec vector DNA in participants who seroconvert via either ADAs or NAb.

The responses of the exploratory endpoints above will be derived as Positive or Negative.

3.4. Baseline Variables

Baseline will be defined as the last value collected prior to the start of study treatment (Day 1) of the interventional study participant.

- Demographic characteristics
 - Gender: Male, Female
 - Race: White, Black or African American, Asian, American Indian or Alaska Native, Native Hawaiian or Other Pacific Islander, Not Reported
 - Ethnic origin: Hispanic or Latino or of Spanish Origin, Not Hispanic or Latino or of Spanish Origin, Not Reported
 - Age (years)
 - Relationship to the interventional study participant
- Physical measurements
 - Weight (kg)
- Medical history will be coded using the most current available version of Medical Dictionary for Regulatory Activities (MedDRA) and will be summarized from the 'Medical History' CRF page.

- Prior Medications at baseline are collected under the 'Concomitant treatments' CRF pages (Visit 1). The World Health Organization (WHO)-Drug coding dictionary will be used to classify concomitant medications.

3.5. Study Conduct and Participant Disposition

3.5.1. Extent of Contact with the Participant in the Interventional Study

- The average number of hours per week that the participant is in the same room as the interventional study participant at visit 1 (screening and baseline visit) is derived as described in Appendix 2.2.
- Total number of days of contact in the same room as the interventional study participant during the first two weeks after administration of study treatment.

3.6. Safety Endpoints

3.6.1. Adverse Events

MedDRA will be used to classify all adverse events (AEs) with respect to system organ class (SOC) and preferred term (PT). Any AE that occurs from the time the participant consents to study participation will be summarized regardless of when the interventional study participant is dosed with study treatment.

3.6.2. Laboratory Data

No safety laboratory tests are performed in this study and analyses for banked biospecimens are out of scope for this SAP.

3.6.3. Concomitant Medications

The WHO-Drug coding dictionary will be used to classify concomitant medications.

4. ANALYSIS SETS (POPULATIONS FOR ANALYSIS)

Data for all participants will be assessed to determine if participants meet the criteria for inclusion in each analysis population prior to releasing the database and classifications will be documented per standard operating procedures.

Only participants who signed informed consent will be included in the analysis sets below.

Population	Description
Immunogenicity	All participants who sign the informed consent document: 1) who are household members of interventional study participants (including siblings) who were assigned to foradistrogene movaparvovec or placebo and received a single dose of study treatment and 2) who have at least one day of contact with the interventional study participant during the first 2 weeks.

5. GENERAL METHODOLOGY AND CONVENTIONS

5.1. Hypotheses and Decision Rules

There is no formal hypothesis testing planned for this study.

5.2. General Methods

For analyses which consider an overall assessment of rates across timepoints, a participant will be considered to have a positive result, if there is at least one positive result after Day 1; similar a participant will be considered to have a negative result if all results after Day 1 are negative.

5.2.1. Presentation of Continuous and Qualitative Variables

Continuous variables will be summarized using descriptive statistics i.e., number of non-missing values N, mean, median, standard deviation (SD), minimum, maximum and first and third quartile (Q1 and Q3).

Qualitative variables will be summarized by frequency counts and percentages.

In case the analysis refers only to certain visits, percentages will be based on the number of participants with non-missing results at that visit, unless otherwise specified.

5.2.2. Analyses for Proportions (%)

The proportion (\hat{p}_t) will be provided for interventional study treatment and each visit.

$\hat{p}_t = \frac{x_t}{n_t}$, where n_t is the number of household contacts in each interventional study treatment and visit and x_t is the number of seroconversion (positive) of household contacts in each interventional study treatment and visit.

5.3. Methods to Manage Missing Data

Unless otherwise specified, all data will be evaluated as observed, and no imputation method for missing values will be used.

Missing statistics, e.g. when they cannot be calculated, should be presented as 'Not applicable' (NA). For example, if N=1, the measure of variability (SD) cannot be computed and should be presented as 'NA'.

6. ANALYSES AND SUMMARIES

6.1. Primary Endpoint

6.1.1. Development of NAb to AAV9

- Analysis Set: Immunogenicity ([Section 4](#))
- Analysis methodology: Descriptive statistics ([Section 5.2.1](#)) by visit and overall
- Missing data: Missing data will not be imputed ([Section 5.3](#))

DMB02-GSOP-RF02 5.0 Statistical Analysis Plan Template 05-Dec-2019

PFIZER CONFIDENTIAL

Page 9

TMF Doc ID: 98.03

- Proportions will be provided separately for visits 3 and 4, and overall at any time during the study by the study treatment (fordadistrogene movaparvovec fordadistrogene movaparvovec or placebo) of the interventional study participant. For overall, the response of the participant will be considered as positive if any values in visits 3 and 4 are positive; otherwise the response will be considered as negative.

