4. STUDY DESIGN

4.1. Overall Design

This single center, low-interventional study to include approximately 50 to 250 participants is designed to estimate the likelihood of developing NAbs to AAV9 because of exposure to shed viral vector material released by a DMD patient treated with fordadistrogene movaparvovec in clinical studies. This study will include participants who live or work in the same household as a patient in one of the fordadistrogene movaparvovec interventional studies which may include Study C3391003, C3391002, C3391008, or C3391001. Given the timing and logistics of the interventional studies, some may have no household contacts participating in C3391007. Up to 5 participants from the same household may be enrolled.

Eligible participants will undergo phlebotomy provided by a Home Health Care Vendor at three home visits as specified in the [Schedule of Activities](#). As a control, seroconversion or rise of antibody titer against other AAVs may also be quantified.

The total duration of participation in the study is approximately 4 months, including up to 48 days for the screening/baseline period and 56 ± 10 days of follow-up after the interventional study patient is dosed with investigational product. The screening/baseline period may be extended if there are delays in the interventional studies.

The single center conducting this study is located in the United States.

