9. STATISTICAL CONSIDERATIONS

9.1. Statistical Hypotheses

There are no hypotheses to be tested.

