9.5. Data Analysis

Detailed methodology for summary and statistical analyses of data collected in this study will be documented in the SAP, which will be dated, filed, and maintained by the sponsor. The SAP may modify the plans outlined in the protocol; any major modifications of primary endpoint definitions or their analyses would be reflected in a protocol amendment.

For the primary, secondary, and each of the exploratory endpoints listed in Section 3, the proportion (and 95% CI) of C3391007 participants will be estimated for 2 groups of participants:

- fordadistrogene movaparvovec: household contacts of patients in interventional studies C3391002, C3391003, C3391001, and C3391008
- placebo: household contacts of patients in interventional studies C3391002 and C3391003

using generalized estimating equations methods with study as covariate to account for correlated responses within the same household. A binomial distribution with a log link and an exchangeable correlation matrix within each household (ie, between any two members of a household the correlation is the same) will be used. Proportions and 95% confidence intervals will be provided separately for each visit (except for Detectable fordadistrogene

movaparvovec vector DNA in participants who seroconvert via either ADAs or NAbs) and overall at any time during the study.

Incidence of AEs will be summarized/listed.

Pharmacogenomic or biomarker data from banked biospecimens will be collected pursuant to local regulations/IRB during or after the trial and retained for future analyses; the results of such analyses are not planned to be included in the CSR.

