7. INTERIM ANALYSES

To enable potentially informing participants and investigators of the estimated seroconversion rate as soon as possible, an independent, external team of statistician(s) and programmer(s) will be established to estimate the seroconversion rates. Only summary seroconversion rates will be communicated. In order to minimize possibility of unblinding internal study team, the external vendor will provide only the percent of participants whose family members received fordadistrogene movaparvovec and converted.

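### SAP V3 drops the 95% confidence interval that the protocol promises for the primary endpoint and puts nothing in its place, in a study sized only on precision

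*SAP*

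**What the plan says.** **Protocol.** For the primary, secondary and exploratory endpoints, section 9.5 states that "the proportion (and 95% CI) of C3391007 participants will be estimated for 2 groups of participants": contacts of treated patients and contacts of placebo patients. The method is a GEE with binomial distribution, log link and exchangeable correlation within household. Results are due at each visit and overall (vector DNA overall only). Section 9.1 states: "There are no hypotheses to be tested". Section 9.2 gives a range of 50 to 250 enrolled and a Table 1 that "shows the expected precision, defined as the upper and lower 95% confidence limits" of the seroconversion proportion. Footnote c to that table reads "Assumes all participants within households and between households are independent". Section 4.1 adds: "Up to 5 participants from the same household may be enrolled".

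**SAP V3 (17 May 2024).** Section 6.1.1 states: "Proportions will be provided separately for visits 3 and 4, and overall at any time during the study by the study treatment". Sections 6.2.1 and 6.3 follow the same pattern. Section 5.2.2 defines the proportion as x over n, where "n_t is the number of household contacts in each interventional study treatment and visit". Section 5.2.1 gives counts and percentages for qualitative variables, and Appendix 4, meant for methodology details, has no content. The version history in section 1 records that the GEE and the 95% CI were removed because few participants were enrolled. For the interim look, section 7 says "the external vendor will provide only the percent of participants whose family members received fordadistrogene movaparvovec and converted".

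**Change control.** Protocol 9.5 and SAP section 2 both say that a major change to the primary analysis will also appear in a protocol amendment. SAP V3 names amendment 1, dated 05 Apr 2022, as its basis. The protocol text still contains the GEE and the interval.

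**The concern.** The study's purpose is to put a number on a risk that families weigh when they consider AAV9 gene therapy for a sibling or other contact. With no test, no decision rule and no power calculation, the confidence interval is its only inferential output. If few or no contacts seroconvert, a table showing 0% can be read as no risk, although the data may be compatible with a substantial one. Small enrolment makes the interval more necessary, not less.

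The GEE was also the plan's only provision for correlation between members of one household. With it gone, nothing in the SAP acknowledges that contacts in the same home share an exposure source, and no household counts are planned from which a reader could make an allowance.

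**Working it through.** **1. Is there an interval anywhere in the current SAP?** Sections 5.2.1, 5.2.2, 6.1.1, 6.2.1 and 6.3 and Appendix 4 contain none. This conflicts with the current text of protocol 9.5. The version history only confirms that the removal was deliberate.

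**2. Reproducing protocol Table 1.** The inputs are two thirds of contacts in the active group and 75% seronegative at baseline (footnotes a and b). For 50 enrolled, n = 50 × 2/3 × 0.75 = 25 in the active group and 50 × 1/3 × 0.75 = 12.5, shown as 13, for placebo. The formula is p ± 1.96 × √[p(1−p)/n], cut at 0. For p = 5% and n = 25, the upper limit is 0.05 + 1.96 × √(0.05 × 0.95/25) = 13.5%, as printed. All 30 intervals (25 active, 5 placebo) match to one decimal, so Table 1 is a normal-approximation table under independence. At zero events this formula gives an interval of zero width, so it is not a suitable replacement.

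**3. An exact interval at small n.** With zero events the Clopper-Pearson upper 95% limit is 1 − 0.025^(1/n). The achieved n is not in the documents, so each n below is an assumption; 25 and 13 are the smallest rows of Table 1.

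| n | Upper limit, 0 conversions |
|---|---|
| 10 | 30.8% |
| 13 | 24.7% |
| 20 | 16.8% |
| 25 | 13.7% |
| 35 | 10.003% |
| 36 | 9.7% |

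Zero conversions therefore leave a true rate above 10% inside the interval for any n up to 35. One conversion in 25 is 4.0% (0.1 to 20.4).

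**4. Allowing for households.** The effective sample size is n / [1 + (m−1) × ICC], where m is the mean number of eligible contacts per household. It replaces n in the formula of step 3. Both m and the ICC are assumptions; the documents give neither.

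| m, ICC | Design effect | n = 25: effective n, upper limit | n = 13: effective n, upper limit |
|---|---|---|---|
| 2, 0.1 | 1.1 | 22.7, 15.0% | 11.8, 26.8% |
| 3, 0.3 | 1.6 | 15.6, 21.0% | 8.1, 36.5% |
| 5, 0.5 | 3.0 | 8.3, 35.8% | 4.3, 57.3% |

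The last row is an extreme. The cap of five applies to enrolled contacts, and at 75% seronegative the expected number eligible is at most 5 × 0.75 = 3.75. With m = 3.75 and ICC 0.5 the design effect is 1 + 2.75 × 0.5 = 2.375, and the limits are 29.6% (n = 25) and 49.0% (n = 13).

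**The case against.** The change is disclosed, a reason is given, and both documents let the SAP modify the protocol's plan. The term major is not defined. The endpoint, the two groups and the visit structure are unchanged, so a move to descriptive reporting could be called minor. This does not rescue the removal. In an estimation study, taking out the only measure of uncertainty is hard to call minor, and the reason given does not explain why a non-model interval was not kept.

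Table 1 sets no precision target, and its independence interval is not the GEE interval of protocol 9.5. Both points are correct, so no stated precision criterion is broken. Both are nevertheless 95% intervals for the same proportion, and Table 1 is the only support offered for the sample size.

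The final tables will show counts, so a reader can compute an exact independence interval. This stands and limits the harm. It does not meet the protocol's commitment, and it does not help with clustering.

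Household correlation does not change x/n, and the proposed Clopper-Pearson interval ignores it too. This is true, so the interval needs a footnote saying so. The clustered figures depend wholly on assumed values, and the top row is an extreme.

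The protocol never promised an interim interval, and the percent-only output protects the blind. That also stands. Recipients of a percent with no denominator can derive no interval, but whether to add one is for the blinding plan.

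**Conclusion.** The concern holds. Protocol 9.5 promises a 95% CI for each group on every endpoint; the current SAP provides none, and small enrolment does not account for that. Dropping the log-link GEE is defensible; dropping every interval is not.

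Under independence, a zero result would carry an upper limit of 13.7% at n = 25 and 24.7% at n = 13. Under the assumed household sizes and correlations the limits run higher, to 29.6% and 49.0% when every household enrols five with 75% seronegative and an ICC of 0.5. These figures illustrate possible outcomes, because neither the achieved n nor any result is in the documents. The conclusion itself depends on none of these assumptions: it follows from setting protocol 9.5 beside SAP 5.2.2 and 6.1 to 6.3.

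**What to change.** **Needed.** In SAP 5.2.2 and 6.1 to 6.3, report x, n and a Clopper-Pearson 95% CI for each group, by visit and overall (protocol 9.5 asks for vector DNA overall only). Add a footnote that the interval assumes independent contacts. State in 5.2.2 that n counts only contacts eligible at baseline for the endpoint concerned; section 3.1 implies this for the primary endpoint, but the formula's definition does not say it. Reconcile protocol 9.5 with the SAP through an amendment or a documented change to the planned analysis.

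**Worth adding.**
- A sensitivity interval using effective sample size n / [1 + (m−1) × ICC], with m the observed mean number of eligible contacts per household and a pre-stated ICC range such as 0.1, 0.3 and 0.5. The range must be fixed in advance because the ICC cannot be estimated when there are no events.
- The number of households contributing and the number with any conversion, as description only.
- The same exact interval beside the interim percent, if the blinding plan accepts that its limits reveal the active-group n.

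**Cost.** SAP wording and a few table columns, with no new data. The intervals will be visibly wide, and the clustered version rests on an assumed ICC.
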